Microbiome study (26) suggested that patients with Th2-low asthma, the same group that responded in the AZISAST study, have a higher microbial burden than patients with the Th2-high phenotype. The AMAZES trial, in contrast, did not distinguish a difference in Th2-high versus Th2-low asthma in the efficacy of azithromycin on exacerbations. Differences in bacterial biomass or composition, all of which may reflect a dysbiotic microbiome, may be one key factor: azithromycin may work in these patients. None of the above-cited studies examined the microbiome, and so a key link to understand how macrolides might benefit patients with poorly-controlled asthma is missing. Neutrophilic asthma, one key Th2-low subtype, is associated with increased bacterial load and pathogens (identified by culture) such as *Hemophilus*, *Pseudomonas*, and *Moraxella* (48). Identifying the correct patient group may be the key to resolving the conflict of whether azithromycin is useful in asthma.

Why would a new study succeed where past, non-selective studies have failed? We hypothesize that in the right asthma phenotype – neutrophil dominant, Th2-low – modifying the dysbiotic microbiome in turn improves clinical control. Our trial will focus on the relation of asthma control to changes in the microbiome induced by azithromycin and understanding the influence of Th2-based phenotypes on this response. By careful examination of the dysbiotic microbiome, careful focus on Th2-low asthmatic patients, and focusing on patients with poor control in which the potential signal is substantial, we will answer the question definitively.

Purpose

The purpose of this protocol is to perform a short-term pilot study so as to acquire data critical to the proper design of a full-scale RCT. The primary objectives of the pilot study are to:

- a) Estimate variability of microbiome composition and diversity over time in control and asthmatic subjects to provide a baseline for the future RCT
- b) Estimate the response of the airway microbiome to azithromycin over time, so that we can generate appropriate power calculations and sample size estimates for the future RCT
- c) Refine our microbial informatics pipeline for the future RCT
- d) Refine our sputum gene expression and cytokine array testing
- e) Test the feasibility of our intervention in a small cohort of subjects with poorly-controlled asthma

Study Design

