This pilot protocol examines the change in the airway microbiome after azithromycin over an 8 week period. 40 subjects with poorly controlled asthma and 10 control subjects with no known lung disease will undergo clinical data collection including ACT score, lung function, exhaled nitric oxide (FeNO), methacholine challenge, and induced sputum and blood collection. Participants with asthma then are randomized 1:1 to receive azithromycin, 250 mg, or placebo, daily for 8 weeks. Clinical parameters including ACT, oral wash, adherence, side-effect profile, spirometry, and biological specimens (sputum, blood, FeNO) are collected again at 4 and 8 weeks. Control subjects undergo the same measurements, but do not receive any intervention.

Schedule of Events

	Asthma (A) or Control (C)	Visit 1/Week 0 (Screening) (+/- 3 days)	Visit 2/Week 4 (+/- 3 days)	Week 6 (+/- 3 days)	Visit 3/Week 8 (+/- 3 days)	Week 10 (+/- 3 days)	Visit 4/Week 12 (+/- 3 days)	Week 14 (+/- 3 days)
Informed Consent	A,C	X						
Site Visit	A,C	X	X		X		X	
Phone Call	A			X		X		X
Confirmation of Eligibility	A,C	X	X					
Randomization	A		X					
Drug Dispensation	A	X ^{1,2}	X ^{1,2,3}		X ^{1,2,3}		X ^{1,2}	
Demographics	A,C	X						
Medical History Review	A,C	X						
Asthma History	A	X						
Smoking History	A,C	X						
Concomitant Medication Review	A,C	X	X		X		X	
Physical Exam/Vital Signs	A,C	X	X		X		X	
Asthma Control Test	A	X						
Demographics Questionnaire	A,C	X						
Family History Questionnaire	A,C	X						
Work Exposures Questionnaire	A,C	X						
Home Exposures Questionnaire	A,C	X						
Physical Activity Questionnaire	A,C	X						
Secondhand Smoke Exposure Questionnaire	A,C	X						
Peak Flow Meter Readings ⁵	A	X	X	X	X	X	X	X
Electronic Diary ⁴	A	X	X	X	X	X	X	X
ECG	A,C	X	X		X		X	
Spirometry with Reversibility ⁶	A,C	X	X		X		X	
Exhaled NO	A,C	X	X		X		X	
Urine Pregnancy Test ⁷	A,C	X						
Methacholine Challenge ⁸	A,C	X	X		X		X	
Sputum Induction	A,C	X	X		X		X	
Oral Wash	A,C	X	X		X		X	
Complete Blood Count with Platelet Count and Differential Blood Sample	A,C	X			X			
Serum IgE Blood Sample	A,C	X						
RAST Blood Analysis	A,C	X						
Research Blood Samples	A,C	X			X			
Adverse Events Review	A,C		X	X	X	X	X	X
Compliance/Adherence to Diary and Study Drugs	A	X	X	X	X	X	X	X

1. Dispensation of albuterol to asthmatic subjects (if required at Visit 2 and Visit 3)
2. Dispensation of ICS/LABA to asthmatic subjects
3. Dispensation of azithromycin/placebo to asthmatic subjects

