11. Electronic Diary. Asthmatic subjects will be asked to complete twice daily diaries in REDCap, a HIPAA-compliant, research oriented database (56). Subjects will receive a hyperlink via email at 7AM and 7PM. The hyperlink directs the subject to the electronic diary contained within REDCap. The diary is designed to require less than 2 minutes of the subjects' time and addresses the following:
 - a. Symptoms from the night before and from the day of
 - b. Physical limitations from the night before and from the day of
 - c. Confirmation of study product dosing
 - d. Peak flow value
12. Peak Flow Meter Readings. Asthmatic subjects will be asked to exhale forcefully into a peak flow meter once in the morning and once in the evening every day. The subject will record the value from the device into the electronic diary.

Asthma medications during the study (Asthma Subjects Only)

Before we begin, we will go over current asthma medications. During this study, we will be providing two asthma medications in a single inhaler, which is guideline-based treatment for the disease severity of the participants in this study. This may be a change from the asthma medicines the subject takes. We will take care that the subjects tolerate the change-over to the new medications. After their participation in this study is finished, we will ask them to see their primary care doctor who, with the subject, will decide which asthma medicines they should be taking at that point.

Starting on the day of visit 1 and continuing through the end of the study, subjects with asthma will receive a standard dosing of two asthma medications in a single inhaler as noted above.

Controller therapy. This will be done using a standard combined single inhaler that contains both an inhaled corticosteroid (fluticasone, 250 mcg) and a long-acting beta-adrenergic agonist (salmeterol, 50 mcg). This is provided in the Advair disk inhaler device and is a device that is familiar to most asthmatic subjects. Subjects use this medication twice daily, generally at about 8 am and 8 pm. The Advair disk has a counter which demonstrates the number of inhalations used by the patient; this number will be recorded by research staff at each in-person visit.

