Rescue therapy. This will be done using a standard preparation of albuterol, 90 mcg per inhalation, per the device ProAir or equivalent metered dose inhaler. This device is familiar to most asthmatic subjects. Subjects use this medication when required for relief of acute asthma symptoms. Subjects will keep a diary card of the use of albuterol and provide this card to research staff at each visit.

Initial, thorough training in the use of each device is done during visit #1 by research staff using the Teach To Goal method implemented by the Asthma and COPD research team at the University of Chicago (63-65). Adherence to and proper technique in the use of each medication will be assessed at each visit, and will be recorded on forms by research staff. Subjects have a 24/7 access to one of the study physicians or other member of the research team for any problems associated with the use of these medications.

Subjects are instructed not to use other asthma medications during the study without informing research staff. The research lead physicians ([name], [name]) or other member of the research team will contact primary care providers when necessary to ensure appropriate asthma care throughout the study. Subjects return to their prescribed asthma medication use at the end of the trial.

Study Drug

Azithromycin. We have received an exemption from the U.S. Food and Drug Administration (FDA) for the use of azithromycin in this protocol. The dose, 250 mg daily for 8 weeks, is a dose and regimen used in other lung diseases such as bronchiectasis, COPD, and cystic fibrosis (33-40).

Participants with asthma who complete the four week run-in phase (visit 1 to visit 2) will enroll at visit 2 into the study drug phase. They will receive the study drug, azithromycin (250 mg once a day for 8 weeks) or blinded placebo through the end of visit 4. They will be provided with a study drug diary. When they return at Visit 4 the study staff will collect the study drug bottle and count drug remaining. At the time of the telephone review (visit 5) subjects with asthma will be asked about any side-effects from azithromycin/placebo use.

Subjects are cautioned about potential side-effects of the drug and reminded about how to contact a study physician or other member of the research team.

Payment

Subjects will receive \$100 at the end of each visit for a total of \$400. This will come in a form of a check which will be mailed to their home.

Risks

Azithromycin

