Long-acting beta agonist therapy (salmeterol): Common: headache, dizziness, lightheadedness, insomnia, nausea, dry mouth and throat irritation.

Short-acting beta agonist therapy (albuterol): Common: nervousness, shaking of a part of the body, headache, irritation of the throat, cough, and muscle, bone or back pain.

Pregnancy

Women of childbearing potential will undergo a pregnancy test on the day of study entry and at each visit. They must have a negative urine pregnancy test to be eligible for study entry. If the

test is positive, the study physician will discuss the matter with the participant. If a participant becomes pregnant before completing the study, they will be asked to notify one of the study doctors immediately. The investigator shall counsel the subject and discuss the risks of continuing with the pregnancy and the possible effects on the fetus. Monitoring of the pregnant subject shall continue until the conclusion of the pregnancy. Pregnancies will be reported to the data and safety monitoring board (DSMB) within one day of the site's awareness. Should the pregnancy result in a congenital abnormality or birth defect, a SAE will be submitted to the IRB, DSMB and NHLBI using the SAE reporting procedures described below.

Confidentiality

Each subject will be assigned a sequential identification number. This number will be linked to the subjects name and data.

We maintain strict confidentiality of all data to minimize the risk of inappropriate access or dissemination of such information. All protected health information including genotype data is saved on a password-protected computer or CRI server in a locked office with limited access. Only staff listed on this protocol will have access to the subjects name and data.

Data sent outside the University of Chicago or Northwestern University, will be sent using an identification number and not the participant's name.

Outcome Measures

Primary:

- ✓ ACT score change from 0 (baseline) to 8 weeks

Secondary:

- ✓ Change in FEV1 from 0 (baseline) to 8 weeks
- ✓ Sputum eosinophils change from 0 (baseline) to 8 weeks
- ✓ Sputum neutrophils change from 0 (baseline) to 8 weeks
- ✓ COMPEX score of asthma severity (from daily diary)
- ✓ Microbiome Shannon alpha-diversity score change from 0 (baseline) to 8 weeks
- ✓ Microbiome beta-diversity score change from 0 (baseline) to 8 weeks
- ✓ Microbiome change in relative proportion of top 10 genera from 0 (baseline) to 8 weeks

Data management

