For demographic and clinical data we use a HIPAA compliant, web-based REDCap data management system residing on a password-protected network. REDCap is a web based, metadata-driven software application developed at Vanderbilt University (Harris et al, 2009) that is maintained by the Center for Research Informatics (CRI) at the University of Chicago. Northwestern University uses the same REDCap system. It allows for range and consistency checks during initial data entry to detect errors, and has built-in features for exporting data into Excel, SAS, STATA, or R files. Files exported from REDCap will be linked to the microbiome data using a unique patient ID number. Double-entry systems will be used to minimize coding error: our experience with our U19 AACRC and with AsthmaNet has found that such double-entry reduces significantly the error-rate in getting information into accessible web forms, and retention

of the paper CRFs ensures proper audit procedures. For biospecimen tracking, we use a web based application with a MYSQL database and a robust security model.

Data and Safety Monitoring Board (DSMB)

The Board will consist of three members at the University of Chicago and at Northwestern University who are not part of this study. Members are [name], [name] (Chair), and [name] (biostatistician). The DSMB will meet every 6 months to review all safety data and make recommendations to the NHLBI regarding continuation of the trial. A copy of the Data Safety and Monitoring Plan (DSMP) is located in Appendix 1.

Statistical analysis

Effect of treatment on clinical outcomes. Descriptive statistics will be generated to summarize the demographic and clinical characteristics of the asthma patients at baseline stratified by treatment arm. To compare changes in clinical parameters of interest, we will perform two-sample t-tests comparing the mean within-subject changes from baseline to 8 weeks. The primary and secondary outcomes measures are listed above.

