For the COMPEX scores, we will determine the time to deterioration as defined in Fuhlbrigge et al (2017). This criteria defines a “diary event” as reaching a predefined change from baseline (threshold) for at least 2 consecutive days, or deterioration in all six variables comprising the COMPEX score over at least a 5-day period plus at least one variable reaching a threshold criterion for at least 2 consecutive days. A “CompEx event” is then defined as the first occurrence of either a diary event or a severe asthma exacerbation (deterioration of asthma leading to oral corticosteroid use, emergency room admission, or hospital admission). Patients who do not experience a CompEx event will be censored as of the last negative assessment. The time from baseline to a CompEx event in days will be compared in the two treatment arms using a logrank test.

Data analysis will be performed using R and STATA software. Linear mixed effects models will be fit for continuous longitudinal outcomes and ordinal, logit, and Poisson mixed effects models will be employed for ordinal, binary, and count responses, respectively (59).

Initial microbiome analysis. Microbiome analysis is done in collaboration with [name], who is Director of The Microbiome Center at the University of Chicago, which houses an advanced sample processing and sequencing core. Samples are partitioned into two aliquots: one for PCR amplification and analysis of the 16S rRNA V4-V5 hypervariable region using amplicon sequencing. We will independently do qPCR of total 16S rRNA of each sputum, oral and nasal sample to determine total load. We will use the Illumina MiSeq platform and barcoded primers to sequence PCR-libraries, and always include non-template and blank controls. The remarkable simplicity of airway microbiota allows a high level of multiplexing (>300 samples per MiSeq flow cell) and ensures 99.99% sequencing coverage after 10,000 reads.

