Power calculations. Power calculations are difficult given the paucity of data about changes in the airway microbiome. This is explicitly an exploratory protocol to ascertain whether, in the short term, treatment of azithromycin in a small cohort of asthmatics changes the lower airway microbiome. We can generate potential power calculations based on the difference in (for example) relative abundance of pathogens in lower airway samples. For this protocol, a key goal is to obtain a good estimate of just how much the microbiome changes in response to azithromycin: if substantial, this trial will aid greatly our ability to make power calculations for larger trials. If changes are small, we will have a clear answer at a modest cost. For example, based on our preliminary published data (25), *Pseudomonas* abundance among asthma patients using ICS was $10.4 \pm 1.8\%$. Assuming 20 evaluable patients on azithromycin in a before and after analysis, we will have 80% power (two-sided $\alpha=0.05$) to detect a change in abundance of $\Delta=0.9$ to $\Delta=1.2$ if the within-patient correlation between pre- and post-treatment abundance is $\rho=0.7$ or $\rho=0.5$. The half-width of the 95% confidence interval for the change in abundance will be 0.7 to 0.84 if $\rho=0.7$ or $\rho=0.5$.

BIBLIOGRAPHY AND REFERENCES CITED

1. (EPR3) EPR. Guidelines for the Diagnosis and Management of Asthma. Bethesda: National Heart Lung and Blood Institute; 2007.
4. Braman SS. The global burden of asthma. *Chest.* 2006; 130(1 Suppl):4S-12S.

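### The primary ACT comparison is an unadjusted t-test on change with no baseline-adjusted analysis named: valid, but generally less precise than it could be

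*Combined protocol and SAP*

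**What the plan says.** Outcome Measures lists one primary outcome, "ACT score change from 0 (baseline) to 8 weeks". Under Statistical analysis (Effect of treatment on clinical outcomes) the method for clinical parameters is "we will perform two-sample t-tests comparing the mean within-subject changes from baseline to 8 weeks", followed at once by a pointer back to the primary and secondary outcomes. No covariate is mentioned.

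Later in the same section the plan adds: "Linear mixed effects models will be fit for continuous longitudinal outcomes". It does not say whether baseline ACT is a response or a covariate, whether the arms share one baseline mean, or how this model ranks against the t-test.

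Three statements bear on what baseline means. Subjects with asthma receive the study controller inhaler "Starting on the day of visit 1 and continuing through the end of the study". Those who complete the four-week run-in "will enroll at visit 2 into the study drug phase". On repeat measurements, Study Design says "Clinical parameters including ACT, oral wash, adherence, side-effect profile, spirometry, and biological specimens (sputum, blood, FeNO) are collected again" at 4 and 8 weeks, whereas the Schedule of Events marks ACT at Visit 1 only.

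**The concern.** A t-test on change subtracts the whole baseline value from the final value, which fixes the baseline slope at 1. The slope that minimises the variance of the treatment contrast is ρ × (final SD / baseline SD), where ρ is the correlation between the two values. Unless that product is close to 1, regression of the final value on arm and baseline gives a tighter estimate from the same patients.

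What is at stake is the width of the ACT interval in a trial of 40 asthma patients, not type I error or bias.

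The choice of baseline visit could affect the size. If week 0 means Visit 1, that ACT value is taken as patients move to the study inhaler and four weeks before study drug. Its correlation with the end-of-treatment value may be lower than that of a Visit 2 value. At equal SDs, a lower correlation is where raw change performs worst.

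**Working it through.** **The plan's own figure.** The only power calculation concerns *Pseudomonas* abundance before and after azithromycin: SD 1.8, 20 patients, two-sided α 0.05, "if the within-patient correlation between pre- and post-treatment abundance is" 0.7 or 0.5. With SD of change = 1.8 × √(2(1−ρ)), that is 1.394 at ρ = 0.7 and 1.800 at ρ = 0.5, paired-t power (19 df) is 0.782 for a change of 0.9 and 0.807 for 1.2. The half-widths are 0.65 (stated as 0.7) and 0.84. The figures reproduce to rounding. They say nothing about ACT, and the two correlations are assumptions about a different variable.

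**Inputs for ACT.** From Study Design: 40 with asthma, 1:1, so 20 per arm if all are evaluable. Not in the documents: ACT SDs, ACT correlation, target difference and dropout. I therefore vary ρ and k = final SD / baseline SD as assumptions.

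**Formulas**, in units of baseline variance:
- contrast on change ∝ 1 + k² − 2ρk
- contrast adjusted for baseline ∝ k²(1 − ρ²) × (N−3)/(N−4), the last factor being the cost of estimating the slope: 37/36 at N = 40

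| k | ρ | change | k²(1−ρ²) | net ratio adjusted/change | simulated ratio |
|---|---|---|---|---|---|
| 1 | 0.3 | 1.400 | 0.910 | 0.668 | 0.669 |
| 1 | 0.5 | 1.000 | 0.750 | 0.771 | 0.773 |
| 1 | 0.7 | 0.600 | 0.510 | 0.874 | 0.877 |
| 1 | 0.9 | 0.200 | 0.190 | 0.976 | 0.980 |
| 1.25 | 0.3 | 1.813 | 1.422 | 0.806 | 0.804 |
| 1.25 | 0.5 | 1.313 | 1.172 | 0.918 | 0.915 |
| 1.25 | 0.7 | 0.813 | 0.797 | 1.008 | 1.008 |
| 1.25 | 0.8 | 0.563 | 0.563 | 1.028 | – |
| 0.8 | 0.3 | 1.160 | 0.582 | 0.516 | 0.512 |
| 0.8 | 0.5 | 0.840 | 0.480 | 0.587 | 0.588 |
| 0.8 | 0.7 | 0.520 | 0.326 | 0.645 | 0.643 |

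The simulation used 40,000 trials of 20 per arm. The row k = 1.25, ρ = 0.8 is the worst case for adjustment: ρk = 1, raw change already uses the best slope, and estimating it costs 37/36, about 3%.

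**Interval half-widths.** In SD units, k = 1, 20 per arm: t × √(2/20) × √(variance factor), with 38 df for change and 37 df for adjusted. At ρ = 0.5, change gives 2.024 × 0.3162 × 1 = 0.640, and adjusted gives 2.026 × 0.3162 × √0.771 = 0.563.

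| ρ | change | adjusted |
|---|---|---|
| 0.3 | 0.757 | 0.620 |
| 0.5 | 0.640 | 0.563 |
| 0.7 | 0.496 | 0.464 |
| 0.9 | 0.286 | 0.283 |

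**Fewer evaluable patients.** At an assumed 16 per arm the factor is 29/28, and the net ratio at k = 1 is 0.777 (ρ = 0.5) and 0.880 (ρ = 0.7).

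**Final value alone against change, k = 1.** The variance ratio is 1/(2(1−ρ)): 0.71 at ρ = 0.3, 1.00 at 0.5 and 1.67 at 0.7. Below ρ = 0.5, subtracting baseline is worse than ignoring it.

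**Do the mixed models close the gap?** Only in some forms. In 20 simulated complete data sets, a random-intercept model with free baseline means and an arm-by-time term gave the difference in mean change to within 1e-14, so it gains nothing. With one common baseline mean, at equal SDs, the variance ratio to change was 0.768 at ρ = 0.5 and 0.865 at ρ = 0.7, close to adjusted regression. The plan does not say which form is meant.

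**The case against.** The strongest reply is that nothing is wrong: the endpoint is defined as change, the t-test tests exactly that, and randomisation makes it valid. Nothing in the trial's aims turns on the lost precision either. The Purpose section opens with "The purpose of this protocol is to perform a short-term pilot study", and its objectives concern microbiome variability and response, laboratory and informatics methods, and feasibility. There is no ACT power claim, and the later trial is to be sized from the Poisson and multivariate models. All of this stands, and it keeps the point modest. It does not make the less efficient choice preferable for the one outcome labelled primary.

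A second reply is that the mixed models may already adjust for baseline. They may, but the text does not commit to it, and it leaves two candidate analyses of the primary outcome unranked.

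A third is that the size is unknown and the equal-SD figures may flatter adjustment. That is fair. Enrolling poorly controlled patients could narrow the baseline spread. Starting from ρ = 0.5 and k = 1, suppose baseline variance halves while the slope (0.5) and residual variance (0.75) stay the same. The change factor is then 0.5² × 0.5 + 0.75 = 0.875, and the net ratio is 0.75/0.875 × 37/36 = 0.881, a 12% cut instead of 23%. From ρ = 0.7 the same step gives 0.51/0.555 × 37/36 = 0.944, a 6% cut instead of 13%. Nor does a lower correlation always count against raw change relative to adjustment: at k = 1.25, going from ρ = 0.9 to 0.8 raises the net ratio from about 0.98 to 1.03. The figures are illustrations and support generally, not always.

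**Conclusion.** The point holds. The sole primary outcome is to be tested by an unadjusted comparison of change, and no baseline-adjusted ACT analysis is named. The cost is precision only. Under the assumed values of ρ and k, adjustment at 20 per arm ranges from a 48% reduction in variance to a loss of about 3%. At equal SDs the reduction is 23% at ρ = 0.5 and 13% at ρ = 0.7. The documents cannot place ACT within that range. The case for change rests on the asymmetry: the worst case is small and bounded, and the possible gain is larger. It is worth doing before data are seen, but it is not a flaw that threatens the trial. No gain is claimed here for FEV1, sputum cells or diversity.

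**What to change.** 1. First reconcile which visits supply the baseline and 8-week ACT values. The Schedule of Events, the Study Design text and the Study Drug section do not agree on this. It is a separate point, needed under either analysis. Name one pre-randomisation visit as baseline for spirometry and sputum as well, since both are scheduled at Visit 1 and Visit 2.
2. Name the primary ACT analysis: linear regression of the end-of-treatment ACT value on randomised arm and baseline ACT value, reporting the adjusted difference with its 95% confidence interval.
3. Keep the two-sample t-test on change as a sensitivity analysis.
4. State that the mixed models are supportive, and say how baseline enters them (as a covariate, or as a response with one common mean across arms).
5. Optionally use the same adjustment for FEV1 and Shannon diversity, and for sputum cells on a suitable scale.

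The analysis change costs one or two SAP sentences and one degree of freedom. It needs no extra patients, and no measurements beyond the ACT values that the endpoint already requires.

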Poisson modeling of relative abundance. To test for differences in relative abundance of key microbial genera between the placebo and azithromycin groups at each time point and over time, we will fit a Poisson regression model with treatment and time as fixed effects with offset (for the total abundance) and with subjects as random effects for the microbial genera of interest (72). Since missing data may be present in the data set, we will create a multiple imputation simulation function in R for generalized linear mixed effects models to improve efficiency of inference and to assess sensitivity of the model over multiple imputations using the R package mice. We will use the specific Poisson regression model to impute the missing values to obtain further efficiency in the data analysis. Based on the Poisson regression model fit, we will make inference for alpha, beta, and gamma diversity measures. These measures will be calculated using either Shannon entropy or the inverse Simpson index (in this context, the habitats of the microbiome genera are the samples collected on the treatment groups over time). Power and sample size calculations for the U01 RCT will be performed based on the fitted Poisson and multivariate regression models. If a test statistic is not significant in the pilot study, we will use mathematical statistical properties of the test statistics (such as the likelihood-ratio, the Wald test, or the score test statistics) under the alternative hypothesis which will allow us to generate power as functions of the sample size. We will create an R package in which we implement all statistical methods in the data analysis work-flow and create R markdown files with fully reproducible data analyses and description of statistical methods. In this way, the data analysis can be easily replicated. If new statistical methods are developed as a result of this complex multi-faceted data analysis, we will write a methodological paper for submission to a statistical journal.

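### The arm comparison of ACT, FEV1 and sputum cells is a change-score t-test with no rule for a missing 8-week value, and the mixed model that could use such patients has no assigned role

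*Combined protocol and SAP*

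**What the plan says.** Outcome Measures lists one primary outcome, "ACT score change from 0 (baseline) to 8 weeks". Changes in FEV1 and in sputum eosinophils and neutrophils over the same interval are secondary.

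Under Effect of treatment on clinical outcomes, the arms are compared as follows: "we will perform two-sample t-tests comparing the mean within-subject changes from baseline to 8 weeks". The next sentence refers back to the listed primary and secondary outcomes. Three other statements bear on the point:

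- Later in the same section: "Linear mixed effects models will be fit for continuous longitudinal outcomes". No outcome, visits, contrast or standing relative to the t-test is given.
- Under Poisson modeling of relative abundance: "Since missing data may be present in the data set, we will create a multiple imputation simulation function". The imputation uses the Poisson model for microbial genera.
- Under Study Design: "Clinical parameters including ACT, oral wash, adherence, side-effect profile, spirometry" and the biological specimens "are collected again at 4 and 8 weeks". The Schedule of Events marks the Asthma Control Test at Visit 1 only.

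COMPEX is handled separately, by a log-rank test with censoring. The sample is "40 subjects with poorly controlled asthma and 10 control subjects with no known lung disease", and "Participants with asthma then are randomized 1:1", which gives 20 per arm. No analysis population, expected dropout or rule for a missing clinical endpoint is stated.

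**The concern.** A within-subject change to 8 weeks does not exist without the 8-week value. With no imputation rule for ACT, FEV1 or sputum cells, a patient who leaves early drops out of the comparison, and so does any value recorded on the way. The test then compares those who stayed, not the arms as randomized.

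Whether this matters depends on who leaves. Differential loss is plausible here: the patients have poorly controlled asthma, and the Risks section lists gastrointestinal effects as common with azithromycin. If poorly responding placebo patients leave, the placebo mean looks too good and the azithromycin effect is understated. If poor responders leave the azithromycin arm, it is overstated. At 20 per arm, 10% dropout is two patients.

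**Working it through.** **The plan's own figure.** There is no power or precision figure for ACT. The only calculation is a one-arm before-after one for *Pseudomonas* abundance, with SD 1.8 and n = 20. The SD of the difference is 1.8·√(2(1−ρ)), which is 1.39 at ρ = 0.7 and 1.80 at ρ = 0.5. A paired t-test then detects 0.92 and 1.19 at 80% power (stated: 0.9 and 1.2), with half-widths 0.65 and 0.84 (stated: 0.7 and 0.84). It reproduces within rounding, but it does not bear on ACT. It does count all 20 azithromycin patients as evaluable, so it allows for no loss.

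**Assumed inputs.** From the documents: 20 per arm, and a baseline, an intermediate and a final value. Assumed: ACT SD 4 at each visit, equal correlation ρ of 0.5 or 0.7 between visits, and a true difference of 2 points at both follow-up visits. The same fraction d leaves each arm before the final visit. On azithromycin they leave at random. On placebo they are those lowest on a score equal to the observed 4-week change plus noise of SD 2. Times are counted from randomization.

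**Formula.** Removing the lowest fraction d of placebo raises the mean 8-week change of those remaining by

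shift = [Cov(score, 8-week change) / SD(score)] × φ(z_d)/(1−d), where Φ(z_d) = d.

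The covariance is 16(1−ρ), and SD(score) = √(32(1−ρ) + 4).

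- ρ = 0.5: 8/√20 = 1.789
- ρ = 0.7: 4.8/√13.6 = 1.302

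The expected completer estimate is 2 minus the shift. The simulated columns come from 6,000 runs per setting.

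| Dropout | φ(z_d)/(1−d) | ρ 0.5, formula | ρ 0.5, simulated | ρ 0.7, formula | ρ 0.7, simulated |
|---|---|---|---|---|---|
| 10% | 0.195 | 1.65 | 1.69 | 1.75 | 1.74 |
| 15% | 0.274 | 1.51 | 1.55 | 1.64 | 1.67 |
| 20% | 0.350 | 1.37 | 1.39 | 1.54 | 1.58 |
| 25% | 0.424 | 1.24 | 1.28 | 1.45 | 1.46 |

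Formula and simulation agree to within 0.04, and repeat simulations moved the figures by at most 0.06. A likelihood estimate that uses the intermediate value averaged 1.98 to 2.02 throughout, with the same or a slightly smaller standard error. The completer loss is 16-36% of the effect at ρ = 0.5 and 13-27% at ρ = 0.7.

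**Bias against noise.** At ρ = 0.5 the SD of change is 4·√(2 × 0.5) = 4. The standard error is 4·√(2/18) = 1.33 with 18 completers per arm and 4·√(2/15) = 1.46 with 15. The bias is 0.31/1.33 = 0.23 of a standard error at 10% dropout and 0.72/1.46 = 0.49 at 25%.

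**A second pattern, in SD units of change.** The worst 10%, 20% or 30% of placebo leave on their observed 4-week response, azithromycin is complete, and the two changes correlate 0.5 to 0.7.

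- Completer bias against azithromycin: 0.09-0.13, 0.16-0.24 and 0.23-0.33 SD.
- Type I error: 6-8%, 8-12% and 11-17% against a nominal 5%.
- Power at a true 0.9 SD: from 79% down to 67-69%, 52-58% and 39-48%.
- Likelihood estimate: bias of 0.01 SD or less.

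**Where the result changes** (first set of assumptions, ρ = 0.5).

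- Random dropout in both arms: the completer t-test averages 1.96-2.03, so no bias.
- The same poor-response rule and fraction in both arms: 1.99-2.04, so no bias.
- Placebo dropout driven by the unseen final value: the completer estimate runs from 1.31 to 0.55 and the likelihood estimate from 1.51 to 0.98. Both are biased, the likelihood estimate less so.

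**The case against.** The plan already names linear mixed models, which keep patients with partial follow-up. That is true, and a reader who infers that the plan considers only completers goes too far. But that sentence is not attached to ACT and is not ranked against the t-test, which is. The multiple imputation is no answer for ACT either, because it belongs to a count model for genera.

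A reader might also infer that every clinical comparison is affected, or that exclusion of patients who withdraw is a written rule. Neither is supported. COMPEX is compared by log-rank test with censoring, and the loss of patients follows from the method, not from a stated rule. The data and safety monitoring plan, cited as Appendix 1, is not among the documents available here, so any follow-up rule in it cannot be checked.

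The timing is also open. The Schedule of Events labels Visit 1 as Week 0, Visit 3 as Week 8 and Visit 4 as Week 12, with randomization at Visit 2. Study Drug describes eight weeks of drug from Visit 2 through Visit 4. By the schedule's labels, a patient who leaves after Visit 3 already has the 8-week value and is not lost, and the 4-week value is taken at randomization. Counted from randomization, 8 weeks is Visit 4. The calculation above assumes the second reading.

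If the schedule governs ACT, there is no intermediate ACT and a mixed model recovers nothing from those who leave. This stands as a precondition of the fix.

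Finally, this is an exploratory pilot with no power claim for ACT, and the bias is at most about half a standard error in the main scenario. That limits the consequence. ACT is still the declared primary outcome, and its estimate will be read as the treatment effect.

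**Conclusion.** The concern holds in a limited form. For ACT, FEV1 and sputum cells, the one comparison tied to the outcome cannot use a patient who lacks the 8-week value, and no rule says what happens to such a patient. A better method is already named in the plan but given no role.

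The size is conditional. One-sided dropout on observed poor response takes a true 2 points to about 1.7 falling to 1.3 (ρ = 0.5) or about 1.8 falling to 1.5 (ρ = 0.7) as dropout goes from 10% to 25%. All of this rests on an assumed SD, effect, correlation and dropout pattern. The tempting stronger reading, that the ACT result will be biased, is not supported: the documents give no dropout rate or pattern, and the bias vanishes when dropout is random or alike in both arms. Nor is the mixed model a full cure, since it only reduces the bias when dropout depends on the unseen endpoint.

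The change should be made, because it is cheap and the primary outcome is involved.

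**What to change.** 1. First reconcile the Study Design text (ACT at 4 and 8 weeks) with the Schedule of Events (ACT at Visit 1 only). Reconcile weeks 0 and 8 in Outcome Measures with the schedule's visit labels and with the drug period in Study Drug.
2. Make the linear mixed model primary for ACT, FEV1 and sputum cells: all randomized asthma patients, all visits from the randomization baseline, treatment-by-visit terms, and the arm contrast at the 8-week endpoint as then defined.
3. Keep the two-sample t-test as a supportive analysis, labelled as completers only.
4. Add a missing-not-at-random sensitivity analysis, for example a delta adjustment applied to the missing endpoint values by arm.

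The analysis changes cost wording and a modest amount of programming. If reconciliation shows that ACT is not yet collected between baseline and endpoint, collecting it adds a short questionnaire at visits that already take place. The statistical price is reliance on a missing-at-random assumption, which is weaker than the missing-completely-at-random assumption under which a completer t-test is generally justified.
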